ACQ-5	Asthma Control Questionnaire, 5-item version
ADA	anti-drug antibody
ATS	American Thoracic Society
BCG	bacille Calmette-Guérin
CompEx	composite of diary events and asthma exacerbations (endpoint)
COPD	chronic obstructive pulmonary disease
DAP	Data Analysis Plan
EC	Ethics Committee
eCRF	electronic Case Report Form
EDC	electronic data capture
eDiary	electronic diary
ERS	European Respiratory Society
FDA	Food and Drug Administration
FeNO	fractional exhaled nitric oxide
FEV ₁	forced expiratory volume in 1 second
FVC	forced vital capacity
HbA _{1c}	hemoglobin A _{1c}
HBcAb	hepatitis B core antibody
HBsAg	hepatitis B surface antigen
HBV	hepatitis B virus
HCV	hepatitis C virus
HIPAA	Health Insurance Portability and Accountability Act
ICH	International Council for Harmonisation
ICS	inhaled corticosteroids
IL	interleukin
IM	intramuscular
IMC	Internal Monitoring Committee
IMP	investigational medicinal product
IND	Investigational New Drug (Application)
IRB	Institutional Review Board
IxRS	interactive voice or web-based response system
LABA	long-acting β-agonist
LAMA	long-acting muscarinic antagonist
LTM	leukotriene modifier
LTRA	leukotriene receptor antagonist

Abbreviation	Definition
MAD	multiple ascending dose
ITT	modified intent-to-treat
NGS	next-generation sequencing
PD ₂₀	provocative dose of methacholine producing a 20% drop in FEV ₁
PD	pharmacodynamic
PEFR	peak expiratory flow rate
PFT	pulmonary function testing
PK	pharmacokinetic
PPD	purified protein derivative
PRO	patient-reported outcome
Q4W	every 4 weeks
QFT-G	QuantIFERON® TB Gold (test)
QTcF	QT interval corrected through use of Fridericia's formula
RBR	Research Biosample Repository
SABA	short-acting β -agonist
SAD	single ascending dose
SAMA	short-acting muscarinic antagonist
TB	tuberculosis
ULN	upper limit of normal
WGS	whole genome sequencing

1. **BACKGROUND**

1.1 **BACKGROUND ON ASTHMA**

Asthma is a chronic inflammatory disease of the airways with an increasing worldwide incidence (To et al. 2012). Approximately 420,000 people die each year as a result of asthma (Global Asthma Network 2018). The pathophysiology of the disease is characterized by variable airflow obstruction, airway inflammation, mucus hypersecretion, and subepithelial fibrosis (NHLBI 2007). Clinically, patients may present with cough, wheezing, and shortness of breath. Despite the development of effective controller therapies for asthma—such as inhaled corticosteroids (ICS), long-acting β -agonists (LABA), and other controller medications—a substantial proportion of patients continue to have uncontrolled symptoms, airflow obstruction, and exacerbations (Bateman et al. 2004; Peters et al. 2006; CDC 2014). Development of new therapies is needed for patients with asthma that remains uncontrolled despite standard-of-care therapies.

Substantial evidence indicates that asthma is not a uniform condition, and there is considerable heterogeneity in clinical characteristics, severity of disease, and underlying biology. The best characterized subtypes consist of those patients in whom the disease is driven by IgE and cytokines expressed by mast cells, type 2 T-helper cells, and type 2 innate lymphoid cells, namely interleukin (IL)-4, IL-5, and IL-13; allergic disease and peripheral eosinophilia are common features. Tryptase is the most abundant secretory granule protein in human lung mast cells and is secreted from mast cells upon activation during inflammatory or allergic responses (Zhang and Timmerman 1997; Payne and Kam 2004). Tryptase is a serine protease and is enzymatically active only in the tetrameric form. Tetrameric tryptase is assembled in the mast cell granule in the presence of heparin and an acidic environment and is released upon mast cell activation/degranulation. Catalytically active extracellular secreted tryptase promotes airway hyper-responsiveness, bronchoconstriction, and amplification of mast cell degranulation (Sommerhoff 2001; He et al. 2004; Bradding and Arthur 2016).

Tryptase levels are elevated in bronchial alveolar lavage fluid and serum of patients with asthma, and correlate with disease severity. Loss-of-function mutations in genes encoding tryptases (*TPSAB1* and *TPSB2*) are common in ethnically diverse populations. These mutations correlate with tryptase activity in vitro, total peripheral tryptase levels in patients with moderate to severe asthma, and clinical response to treatment with the anti-IgE antibody omalizumab (Choy et al. 2018). As these mutations determine expression of functional tryptase, they may predict clinical outcomes for inhibitors of tryptase activity. Multiple small molecule inhibitors blocking tryptase function have shown efficacy in rodent and sheep models of allergic asthma (Clark et al. 2001). In addition, a small molecule inhibitor of tryptase, APC 366, has been shown to exhibit clinical activity by attenuating inhaled allergen-induced late asthmatic response in patients with mild atopic asthma (Krishna et al. 2001).

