- Diary worsening is based on the occurrence of prespecified changes (deteriorations) in the following six parameters: morning PEFR, evening PEFR, morning symptom score, evening symptom score, morning short-acting rescue therapy use, and evening short-acting rescue therapy use. Deterioration criteria, defined as either a change from baseline (threshold) or worsening of a certain magnitude (slope) over 5 consecutive days, are presented for each parameter in the protocol. Diary worsening is defined as occurrence of one or both of the following scenarios:
 - Patient meets threshold deterioration criterion (i.e., prespecified change from baseline) for PEFR (morning and/or evening) and at least one other parameter (i.e., morning symptom score, evening symptom score, morning rescue therapy use, and/or evening rescue therapy use) on 2 consecutive days.
 - Patient meets threshold deterioration criterion (i.e., prespecified change from baseline) for one parameter on 2 consecutive days and slope deterioration criterion (i.e., prespecified change over 5 consecutive days calculated via univariate linear regression) for all six parameters.

For the purposes of determining whether the threshold deterioration criteria are met, baseline levels are calculated for each individual as the mean over the 10 planned sessions conducted prior to time of randomization for each of the diary variables.

In the event that the first diary worsening scenario is met (i.e., threshold met in two parameters), the diary worsening event will start on the first of the 2 consecutive days (defined as Event Days 0 and 1).

In the event that the second diary worsening scenario is met (i.e., threshold in one parameter and slope in all six parameters), the diary worsening event will start on the first of the 2 consecutive days that the threshold was met (Event Days 0 and 1), and the slope criteria for the six parameters must be met on Day 0 and the 4 consecutive days prior to that day (i.e., Event Day -4 through Event Day 0).

To qualify for the second diary worsening scenario, data from at least 3 of the 5 consecutive days must be available for calculation of the slope for each parameter. Analyses will be based on observed asthma exacerbations and diary worsenings, with no imputation for premature discontinuation or missing diary entries.

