The primary endpoint will be analyzed through use of a Cox proportional hazards regression model comparing MTPS9579A with placebo with respect to time to first CompEx event, with adjustment for baseline covariates. Estimated hazard ratios and their associated 95% confidence intervals will be provided. Further details regarding the primary endpoint and the analysis will be described in the Data Analysis Plan.

Determination of Sample Size

The primary goal of this trial is estimation rather than hypothesis testing. This is largely due to the uncharacterized distribution of CompEx in the placebo arm. The interim analysis based upon 51 events will yield reasonable precision for estimating the true underlying hazard ratio.

Interim Analyses

An interim analysis will take place after approximately 51 patients have experienced a CompEx event in this study. The expected timing of the interim analysis will be approximately 60 weeks after the first patient is randomized. No formal stopping rules or decision criteria have been defined for the result of the interim analysis.

The interim analysis will be performed and interpreted *for potential enrollment decisions (e.g., temporary or permanent enrollment halt, change to number of total randomized patients), for early study termination, or for administrative purposes (e.g., planning of future studies)* by members of the Sponsor study team and appropriate senior management personnel, who will be unblinded at the treatment group level.

Access to treatment assignment information will follow the Sponsor's standard procedures.

Given the hypothesis-generating nature of this study, the Sponsor may choose to conduct up to two additional interim efficacy analyses. The decision to conduct an optional interim analysis and the timing of the analysis will be documented in the Sponsor's trial master file prior to the conduct of the interim analysis. The interim analysis will be performed and interpreted *for potential enrollment decisions (e.g., temporary or permanent enrollment halt, change to number of total randomized patients), for early study termination, or for administrative purposes (e.g., planning of future studies)* by members of the Sponsor study team and appropriate senior management personnel, who will be unblinded at the treatment group level. Access to treatment assignment information will follow the Sponsor's standard procedures.

LIST OF ABBREVIATIONS AND DEFINITIONS OF TERMS

Abbreviation	Definition

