6.4 EFFICACY ANALYSES

Efficacy analyses will be conducted on an mITT population, consisting of all randomized patients who received at least one dose of study drug during the 48-week double-blind treatment period, with patients grouped according to the treatment assigned at randomization.

Unless otherwise noted, analyses of efficacy outcome measures will be adjusted by blood eosinophil level (Visit 1 < 150 cells/ μ L, 150–300 cells/ μ L, > 300 cells/ μ L) and geographic region (United States/Western Europe, Eastern Europe, Southern Hemisphere).

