In the event that the second diary worsening scenario is met (i.e., threshold in one parameter and slope in all six parameters), the diary worsening event will start on the first of the 2 consecutive days that the threshold was met (Event Days 0 and 1), and the slope criteria for the six parameters must be met on Day 0 and the 4 consecutive days prior to that day (i.e., Event Day –4 through Event Day 0).

To qualify for the second diary worsening scenario, data from at least 3 of the 5 consecutive days must be available for calculation of the slope for each parameter. Analyses will be based on observed asthma exacerbations and diary worsenings, with no imputation for premature discontinuation or missing diary entries.

The primary endpoint will be analyzed through use of a Cox proportional hazards regression model comparing MTPS9579A with placebo with respect to time to first CompEx event, with adjustment for baseline covariates as described in Section 6.4. Estimated hazard ratios and their associated 95% confidence intervals will be provided. Further details regarding the primary endpoint and the analysis will be described in the DAP.

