## Tables

### Output 3.1 Time to First CompEx Event, 48-Week Double-Blind Treatment Period

Protocol: GB41149

Analysis Population: Modified Intent-to-treat population (MITTFL = 'Y')

Time to First CompEx Event, 48-Week Double-Blind Treatment Period, mITT Subjects Who Were Dosed in Treatment Period		
	Placebo	MTPS9579A Active
Total number of patients per arm	XX	XX
Patients with event: N (%)	XX (XX.X%)	XX (XX.X%)
Patients with diary event: N (%)	XX (XX.X%)	XX (XX.X%)
Patients with exacerbation: N (%)	XX (XX.X%)	XX (XX.X%)
Patients without event (%)	XX (XX.X%)	XX (XX.X%)
Time to event (weeks)		

Median	XXX.X	XXX.X
95% CI	(XXX, XXX)	(XXX, XXX)
25 - 75 percentile	XXX, XXX	XXX, XXX
Range	XXX to XXX	XXX to XXX
Stratified Analysis		
p-value (log-rank)	-	X.XXXX
Hazard Ratio	-	X.XX
95% CI	-	(XX.X, XX.X)
p-value	-	X.XXXX

Hazard ratios were estimated by Cox regression with the following stratification factors as covariates: blood eosinophil level at visit 1 (<150, >=150 to <=300, >300 cells/uL), number of asthma exacerbations requiring the use of systemic corticosteroids within the 12 months prior to the study entry (1 or >=2 events), and geographic region (United States/Western Europe [United States, Germany], Eastern Europe [Poland], Southern Hemisphere [Peru, Argentina]).

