Footnotes: Estimates are based on a mixed model for repeated measures (MMRM) analysis with an unstructured covariance matrix. The model used the absolute change pre-bronchodilator FEV1 as the response variable and included terms for treatment arm, study visit, treatment arm by study visit interaction, baseline FEV1 as well as its interaction with study visit, in addition to the stratification factors: blood eosinophil level at visit 1 (<150, >=150 to <=300, >300 cells/uL), number of asthma exacerbations requiring the use of systemic corticosteroids within the 12 months prior to the study entry (1 or >=2 events), and geographic region (United States/Western Europe [United States, Germany], Eastern Europe [Poland], Southern Hemisphere [Peru, Argentina]). Subjects without valid baseline values are excluded from analysis.

N in the header represents the number of subjects with at least one post-baseline value.

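### The primary CompEx Cox model leaves out the diary baselines already derived for each patient, which gives up some power if those baselines are prognostic

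*Protocol*

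**What the plan says.** - **Primary model.** The Protocol Synopsis (Primary Analysis) specifies a "Cox proportional hazards regression model comparing MTPS9579A with placebo with respect to time to first CompEx event, with adjustment for baseline covariates". Protocol 6.4.1 repeats this, "with adjustment for baseline covariates as described in Section 6.4".
- **Covariates.** Protocol 6.4 states: "Unless otherwise noted, analyses of efficacy outcome measures will be adjusted by blood eosinophil level", and adds geographic region. It names nothing else. SAP Section 3 adds exacerbations in the prior year. The footnote to SAP Output 3.1 reads "Hazard ratios were estimated by Cox regression with the following stratification factors as covariates" and then lists eosinophil group, prior exacerbations (1 or ≥2) and region. (SAP Section 3 takes eosinophils at Week 2 and the footnote at Visit 1. That is a separate matter.)
- **Diary baselines.** For the thresholds, "baseline levels are calculated for each individual as the mean over the 10 planned sessions conducted prior to time of randomization", separately for each diary variable (Protocol 6.4.1).
- **Thresholds.** Protocol Appendix 8 sets PEFR at 15% below baseline, rescue use at 1.5 times baseline, and symptom score at 1 above baseline or the scale maximum.
- **Other efficacy models.** The FEV1 repeated-measures model includes "baseline FEV1 as well as its interaction with study visit" (footnote to SAP Output 3.6). The absolute-change model in Output 3.8 does the same for FeNO.
- **Setting.** Protocol 6.1 gives estimation as the main goal and cites 51 events for the interim analysis. Protocol Section 6 sets two-sided tests at 0.2. SAP Output 1.1 shows 65 placebo and 69 active patients in the mITT population.

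**The concern.** Six diary variables drive the diary component of the primary endpoint. Their baselines are measured before randomization and already derived, so they are natural candidates for adjustment. A patient's baseline also helps to decide how easily a threshold is met. For example, suppose the five symptom responses are scored 0 to 4 (an assumption). A patient with a mean of 2.0 then needs a 3, one with 2.1 needs a 4, and one above 3 can qualify through the maximum with a rise of less than 1.

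If baseline severity is prognostic and is left out of a Cox model, the treatment coefficient shrinks towards zero while its standard error hardly changes, so power falls. A chance imbalance in baseline severity between 65 and 69 patients would also go uncorrected. With enrollment closed, analysis is one of the few places left to recover power.

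**Working it through.** **What the plan's own figure implies.** The visible text of Protocol 6.1 gives 51 events but no target hazard ratio, power or interval width, and the rest is redacted. So there is no stated result to reproduce. From 51 events at 1:1:

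- SE(log HR) = 2/√51 = 0.280.
- The 95% interval is the HR divided and multiplied by exp(1.96 × 0.280) = 1.73.
- For an assumed HR of 0.65, power at two-sided 0.2 is Φ(0.4308/0.280 − 1.282) = Φ(0.256), about 0.60.

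**Simulation A: one prognostic baseline against no covariates.** 65 versus 69 patients; exponential times censored at 48 weeks; placebo 48-week risk 0.48 (assumed), giving about 55 events; true HR 0.65 (assumed); standard normal baseline score; 3,000 trials per setting. The gain in event-equivalents is (mean adjusted Z / mean unadjusted Z)², because Z² grows in proportion to events.

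| Assumed log HR per SD | Mean unadjusted HR | Gain | Power, unadjusted → adjusted |
|---|---|---|---|
| 0.3 | 0.65 | 4% | 62% → 62% |
| 0.5 | 0.66 | 11% | 60% → 63% |
| 0.7 | 0.68 | 25% | 56% → 62% |

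At strength 0 the gain is 0%. The last row can be checked by hand: (ln 0.65 / ln 0.68)² = (0.4308/0.3857)² = 1.25. Power at HR 0.68 with 51 events is Φ(0.3857/0.280 − 1.282) = Φ(0.095), about 0.54, which is 6 points below 0.60.

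**Simulation B: closer to the actual choice.** The comparison model already holds covariates of the planned type. Two terms are added, one prognostic and one pure noise.

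| Assumed log HR per SD | Gain | Power, planned → with diary terms |
|---|---|---|
| 0 | about 0% | 64% → 64% |
| 0.3 | about 4% | 60% → 61% |
| 0.5 | about 14% | 60% → 65% |
| 0.7 | about 31% | 57% → 64% |

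Read each row across. Small differences between rows are within simulation error.

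**Standard error.** It does not fall. In a set-up like A, mean SE(log HR) without and with the baseline was 0.272 and 0.274, 0.270 and 0.272, and 0.266 and 0.268 at strengths 0.3, 0.5 and 0.7. In B it rose slightly each time, for example from 0.275 to 0.280, which takes the 95% factor from exp(1.96 × 0.275) = 1.71 to exp(1.96 × 0.280) = 1.73.

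**Parameters.** The SAP model has 1 (treatment) + 2 (eosinophils) + 2 (region) + 1 (prior exacerbations) = 6, or 51/6 = 8.5 events per parameter. Two diary terms make 8: 51/8 = 6.4, or 56/8 = 7.0 with 56 events. All six diary means would make 12: 51/12 = 4.25. In a further simulation at 51 events, six diary terms raised the SE from about 0.284 to 0.293–0.295.

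**The case against.** **The interval does not get shorter.** A reader might infer that the plan throws away precision. It does not. In a Cox model the gain is a coefficient further from zero, not a smaller SE. Since the stated goal is estimation, this counts against making much of the point, and it stands.

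**The planned hazard ratio is not wrong.** The gap between 0.65 and 0.66 or 0.68 reflects conditioning on fewer covariates. It is also small beside a 95% factor of 1.73.

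**Relative thresholds do not prove that baseline predicts the event.** A reader might infer that the dependence holds by construction for every event. The documents do not support that:

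- The symptom criterion has an absolute-maximum alternative.
- The slope criterion does not use the baseline, although its scenario also needs one threshold.
- The exacerbation component does not use it at all.
- Crossing the rescue threshold alone is not an event: scenario 1 also needs PEFR, and scenario 2 needs slopes in all six parameters.
- Scoring against baseline already removes part of the difference between patients, and worse baseline disease could act in opposite directions on the two components.

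The net strength is unknown and could be near zero.

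**The FEV1 and FeNO comparison is loose.** Those outcomes have a single baseline of their own, and a composite time-to-event endpoint does not. The comparison shows only that the plan accepts baseline adjustment where it is available.

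**Planned covariates may already carry the information.** Overlap would shrink the gain. Prior exacerbations may add little, however: Protocol 4.1.1.1 requires at least two, so a split at 1 versus ≥2 should be nearly constant among eligible patients.

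**Timing.** Protocol 6.9.1 allows the study team to be unblinded at treatment-group level at the interim. Changing the primary model after such a look would be hard to defend. This stands, and it limits the fix.

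**Conclusion.** The omission is plain in both documents: no diary baseline enters the CompEx model. Its cost depends on a prognostic strength that the documents do not give. For assumed values of 0.3 to 0.7 in log HR per SD and a true HR of 0.65, it is slight attenuation and roughly 4% to 30% in event-equivalents. At 51 events that is 51 × 0.04 ≈ 2 to 51 × 0.30 ≈ 15 events, or about 1 to 7 points of power at two-sided 0.2. At zero strength the cost is about nil. This is a cheap improvement worth making, not a flaw that invalidates the planned analysis.

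**What to change.** In Protocol 6.4 and 6.4.1, SAP Section 3 and the Output 3.1 footnote:

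1. Add two continuous covariates to the CompEx Cox model: baseline mean symptom score and log(1 + baseline mean rescue use). State how the morning and evening means are combined.
2. State how puffs and nebulizer uses are put on one scale. Protocol Appendices 4 and 5 record them separately and give no conversion.
3. Consider baseline PEFR as well, since scenario 1 requires it. Do not add all six diary means.
4. Keep every planned covariate, including the prior-exacerbation factor, and report the current model alongside.
5. If treatment-group results have already been seen at an interim analysis, label the diary-adjusted model supportive and keep the current model primary.

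No new data are needed, only SAP wording and one more model run. The price is two more parameters (about 8 for 51–56 events), a slightly larger SE, and a hazard ratio conditional on two more baseline values, which the report should state.

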1.2 BACKGROUND ON MTPS9579A

MTPS9579A is a full-length humanized IgG4 antibody that binds with high affinity to human and cynomolgus monkey tryptase. MTPS9579A inhibits tryptase activity by irreversibly dissociating the active tetramer into inactive monomers. MTPS9579A is currently under clinical investigation in a Phase Ia/b dose-escalation trial (GA40396) in approximately 106 healthy volunteers. The dose has been escalated in both single ascending dose (SAD) and multiple ascending dose (MAD) cohorts up to a maximum of 3600 mg IV for SAD or MAD (every 4 weeks [Q4W] for 3 doses). In addition, a Phase Ic study is planned to evaluate the pharmacokinetic (PK) and pharmacodynamic (PD) relationships of MTPS9579A in the lung using bronchoscopy in patients with asthma after a single dose. MTPS9579A has been well tolerated at all dose levels, with no serious adverse events and only one adverse event leading to discontinuation—a volunteer who developed Grade 2 increased blood creatine phosphokinase. All reported adverse events in 106 healthy volunteers have been Grade 1 or 2, and most events resolved without requiring treatment. After administration of MTPS9579A in these healthy volunteers, active tryptase measurements from the nasal mucosal lining fluid decreased below detection levels. Greater than 95% target inhibition is anticipated in patients with asthma at the proposed dose of 1800 mg IV Q4W.

Refer to the MTPS9579A Investigator's Brochure for details on nonclinical and clinical studies.

